## 5. ANALYSIS POPULATIONS

Data will be summarized using the following analysis populations.

- All Enrolled Subjects: This analysis population will include all enrolled subjects, regardless of whether they received any amount of study drug. The all enrolled subjects population will be used for the summarization of subject disposition.
- Safety Population: This analysis population will include all enrolled subjects who have received any dose of study drug. The safety population will be used for the analysis of safety measures.
- Efficacy Population: This analysis population will include all enrolled patients who have received at least one dose of the study drug and who do not have EGFR or ALK mutant tumors.
- Primary Efficacy Population: This analysis population will include all efficacy population subjects, excluding patients who have not received surgery after neoadjuvant treatment with Atezolizumab, and excluding subjects who have not had a complete resection. This population will be used for primary efficacy analysis. For the primary efficacy population, if major pathological response is unable to be assessed, then it will remain undetermined and the subject will be removed from this population.

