Hilar and mediastinal lymph node dissection or sampling should be performed. For right sided resections, this involves at least lymph nodes from levels 4R, 7, 10R, and 11R. For left sided resections, this involves at least lymph nodes from levels 5/6, 7, 10L, and 11L. Patients in whom a complete resection is not achieved will be discontinued from the study and will be replaced.

Pathologic specimens will undergo standard histopathologic and immunohistochemical evaluation for lung cancer. Tumor, normal lung parenchyma, and draining lymph nodes will be harvested immediately after resection. Sections of tumor will be fresh frozen and formalin-fixed for correlative studies (see [Appendix 3](#)). Sections of lymph nodes will be freshly prepared in media and formalin-fixed for correlative studies. Sections of adjacent normal lung tissue will be formalin-fixed for correlative studies. Sections of tumor, adjacent normal lung tissue and lymph node may be freshly dissociated for correlative studies.

Whole blood samples will be collected at the time of surgical resection for correlative studies. The blood will be used for IMMUNOME and processed for PBMC, plasma, and serum for correlative studies.

At the postoperative follow-up visit, patients whose tumors have not demonstrated evidence of pathologic response or who have radiographic progression will have an end-of-study treatment (atezolizumab) visit, after which they will enter Surveillance for 2 years then Survival Follow-up for 1 year.

Whole blood will be collected at postoperative follow-up visit and will be processed for plasma, serum, and PBMC for correlative studies.

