4.6 PATIENT, TREATMENT, STUDY, AND SITE DISCONTINUATION

4.6.1 Patient Discontinuation

Patients have the right to voluntarily withdraw from the study at any time for any reason. In addition, the investigator has the right to withdraw a patient from the study at any time. Reasons for withdrawal from the study may include, but are not limited to, the following:

- Patient withdrawal of consent at any time
- Any medical condition that the investigator or Sponsor determines may jeopardize the patient's safety if he or she continues in the study
- Investigator or Sponsor determines it is in the best interest of the patient
- Patient non-compliance

Every effort should be made to obtain information on patients who withdraw from the study but do not withdraw consent. The primary reason for withdrawal from the study should be documented on the appropriate eCRF. However, patients will not be followed for any reason after consent has been withdrawn. Patients who withdraw from the study will not be replaced.

If a patient withdraws from the study, the study staff may use a public information source (e.g., county records) to obtain information about survival status.

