4.6.2 Atezolizumab Treatment Discontinuation

Patients must discontinue neoadjuvant or adjuvant atezolizumab treatment if they experience any of the following:

- Pregnancy
- Radiographic disease progression and/or symptomatic deterioration attributed to disease progression as determined by the investigator after integrated assessment of radiographic data, biopsy results, and clinical status. Please note all radiographic images related to disease will be collected.
- Intolerable toxicity related to atezolizumab, including development of an irAE determined by the investigator to be unacceptable given the individual patient's potential response to therapy and severity of the event. May contact Medical Monitor and Sponsor for further guidance.
- Any medical condition that the investigator or Sponsor determines may jeopardize the patient's safety if he or she continues on atezolizumab
- Use of another non-protocol-specified anti-cancer therapy

The primary reason for atezolizumab discontinuation should be documented on the appropriate eCRF.

If patient prematurely discontinues neo-adjuvant treatment for any reason other than progressive disease (after Cycle 1 and before surgery), they may proceed with surgery as part of the study and enter surveillance. If patient discontinues treatment for any

reason after surgery, they should remain in Surveillance until they complete 2 years and then move to Survival Follow-up. Patients who discontinue atezolizumab prematurely will not be replaced.

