6.4.1 Primary Efficacy Endpoint

The effectiveness of the atezolizumab will be assessed by major pathologic response rate in the efficacy population, excluding patients who have not received surgery after neoadjuvant treatment with atezolizumab. A statistical test of a single proportion of major pathologic response rate will be tested against the alternative that the rate is 15%. If the null hypothesis is rejected then this is evidence that the response rate exceeds 5% when atezolizumab is given before resection. The one-sided 95% confidence interval (CI) for major pathologic response will be reported.

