### 6.3.2 Secondary Efficacy Analysis

The proportion of subjects who experienced a major pathologic response in the PD-L1 positive group (TC123IC123) and PD-L1 (TC0IC0) negative group will be compared using the Pearson's chi-square test in the primary efficacy population. If the number of subjects in one of the table cells is less than 5, then Fisher's exact test will be used instead. The lower bound of the 80% Wald CI for the difference in proportions between the two groups will be obtained. The number and the proportion of subjects with major pathologic response will be summarized by PD-L1 positive group (TC123IC123) vs. PD-L1 negative group (TC0IC0).

A similar analysis will also be performed for objective response rate: the proportion of subjects who are objective responders (Complete Response and Partial Response are considered as responders, Stable Disease, Progressive Disease and Not Evaluable are considered as non-responders) in the PD-L1 positive (TC123IC123) and negative (TC0IC0) groups will be compared using Pearson's chi-square test in the efficacy population. If the number of subjects in one of the table cells is less than 5, then Fisher's exact test will be used instead. The lower bound of the 80% Wald CI for the difference in proportions between the two groups (PD-L1 positive (TC123IC123) and negative (TC0IC0)) will be obtained. The number and proportion of subjects who are objective responders will be summarized by PD-L1 positive (TC123IC123) and negative (TC0IC0) groups.

A forest plot of major pathological responders will be produced, including the following categories:

- Sex
- Race
- Ethnicity
- ECOG performance status
- Non-metastatic lung cancer histology
- Initial diagnosis staging
- PD-L1 positive (TC123IC123) and PD-L1 negative (TC0IC0)

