### 6.6 Changes to Methods Planned in the Protocol

There is no change in the SAP which is deviate from protocol.

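### SAP section 5 drops incompletely resected and unscorable patients from the primary MPR denominator and from DFS, SAP 6.6 declares no change, and the SAP text plans no MPR rate for treated patients

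*SAP*

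**What the plan says.** **Primary MPR set.** Protocol 6.4.1 assesses the "major pathologic response rate in the efficacy population, excluding patients who have not received surgery after neoadjuvant treatment with atezolizumab". That is its only exclusion. SAP section 5 defines a Primary Efficacy Population by "excluding patients who have not received surgery after neoadjuvant treatment with Atezolizumab, and excluding subjects who have not had a complete resection", and adds that "if major pathological response is unable to be assessed, then it will remain undetermined and the subject will be removed from this population". SAP 6.3.1 and Table 14.2.1 use this set.

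**Declared changes.** SAP 6.6 states: "There is no change in the SAP which is deviate from protocol".

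**Replacement.** Protocol 3.1.2 says: "Patients in whom a complete resection is not achieved will be discontinued from the study and will be replaced". Other losses are treated differently. Protocol 4.6.1 says "Patients who withdraw from the study will not be replaced", and 4.6.2 says "Patients who discontinue atezolizumab prematurely will not be replaced".

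**Unevaluable radiographic response.** For the objective response rate, SAP 6.3.2 rules that "Stable Disease, Progressive Disease and Not Evaluable are considered as non-responders".

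**DFS.** The DFS definition in SAP 6.3.3 and Table 14.2.3.2 use the Primary Efficacy Population. The Kaplan-Meier paragraph of SAP 6.3.3 names the efficacy population for OS, DFS and EFS alike. Protocol 6.4.3 restricts DFS to operated patients, and its last paragraph names the efficacy population for the Kaplan-Meier analyses.

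**MPR by PD-L1.** SAP 6.3.2 uses the Primary Efficacy Population. Protocol 6.4.2 and SAP Table 14.2.2.1 use the efficacy population. Figure 1.1, the forest plot of MPR, is also labelled with the efficacy population.

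**The concern.** The denominator of the primary endpoint is narrower in the SAP than in the protocol, yet the section meant to record such differences says there are none. One of the two added exclusions, unscorable MPR, has no counterpart in the protocol. It also runs opposite to the SAP's own rule for radiographic response.

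The SAP text plans no overall MPR rate, test or interval for treated patients in which those who never reached surgery, or gave no scorable specimen, count as failures. A reader of the primary table therefore learns the rate among completely resected, scorable patients, and cannot read off the rate among patients who started treatment.

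The narrowing carries into DFS. A completely resected patient with an unscorable specimen leaves the DFS analysis, although DFS runs from surgery to recurrence or death and needs no MPR score. Two paragraphs of SAP 6.3.3 then name different DFS sets, and SAP 6.3.2 and Table 3 name different sets for MPR by PD-L1. A programmer would have to choose.

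**Working it through.** **The plan's own figure.** The final rule is at least 17 responders with 180 enrolled (protocol 6.1, SAP 6.1.4: null rate 5%, one-sided 0.05, variance under the alternative of 15%). The boundary is 180 × (0.05 + 1.645 × √(0.15 × 0.85 / 180)) = 16.88, so 17. This reproduces. SAP 6.3.1 specifies a one-sample exact binomial test against 5%, so the decisions below use that test.

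**Inputs that are assumed.** The documents do not say how many patients each exclusion removes. I assume 160 treated patients in the efficacy population, 152 of them operated (the protocol set), and SAP sets of 149, 144 or 136.

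**Estimate, 17 responders, none among those removed.** Rate = 17/N, with the one-sided 95% Clopper-Pearson lower bound.

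| Set | N | Rate | Lower bound |
|---|---|---|---|
| Treated | 160 | 10.6% | 6.9% |
| Operated (protocol) | 152 | 11.2% | 7.25% |
| SAP | 149 | 11.4% | 7.4% |
| SAP | 144 | 11.8% | 7.7% |
| SAP | 136 | 12.5% | 8.1% |

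The protocol's own no-surgery exclusion accounts for 11.18 − 10.62 = about 0.6 points. The SAP exclusions add 0.2, 0.6 and 1.3 points beyond that.

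**The same with one responder among those removed.** An incompletely resected patient still has a resection specimen, which can be scored and can show MPR. If one of the 17 responders is such a patient, the SAP set of 144 gives 16/144 = 11.1%, against 17/152 = 11.2% in the protocol set. The SAP rate is then not higher.

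**Decision by the exact test, protocol set of 152 against the SAP sets.**
- 13 responders: p = 0.042 at 152. The test already rejects in the protocol set, and removing non-responders only lowers p.
- 12 responders: p = 0.080 at 152, 0.058 at 144, 0.051 at 141, 0.049 at 140 and 0.041 at 136. The decision changes only at N of 140 or less, that is, once at least 152 − 140 = 12 operated patients are removed with no responder among them.
- 11 responders: the largest N at which the test rejects is 125, below every set considered.

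So the SAP-only exclusions change the decision at exactly 12 responders and nowhere else in this scenario. If the count of 17 governs instead, it is a count without a denominator, and under the same assumption the exclusions change no decision.

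**Can the supportive analysis carry weight?** With 160 treated, the exact test rejects at 14 or more (size 0.0305). If the true rate is 15% among those kept and zero among those removed, the rate among treated is 0.15 × share kept. Power is then 97.5%, 95.5% and 92.2% with 10%, 15% and 20% removed.

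**The case against.** The strongest reply is that the SAP implements the protocol. Replacing incompletely resected patients, while withdrawals and early discontinuations are not replaced, makes most sense if they leave the evaluable set. This largely stands: the first exclusion is a reasonable reading of protocol 3.1.2. But that is a conduct rule, protocol 6.4.1 does not carry it into the denominator, and SAP 6.6 should say so.

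On unscorable MPR, the protocol is silent and leaves detail to the SAP, and removal fits the default in SAP 6.1.1 of basing percentages on non-missing data. That makes it a gap filled rather than a rule broken. It is still a choice about the primary denominator that deserves an entry and a reason, given the opposite choice for radiographic response.

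On DFS, starting the clock at the first disease-free date supports the restriction to complete resection, and protocol 6.4.3 itself names two sets. Both points stand. What remains is the loss of completely resected patients for want of an MPR score.

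The table shells were not available, so an overall row on the efficacy population in Table 14.2.2.1 or Figure 1.1 cannot be ruled out. Listing 16.2.6.1 gives patient-level pathological response on that population. The point is limited to what the SAP text plans.

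**Conclusion.** The point holds as a cheap improvement. The mismatch between protocol 6.4.1 and SAP section 5, the inaccurate statement in SAP 6.6, and the conflicting populations for DFS and for MPR by PD-L1 are plain on the text. The numerical size rests on assumed counts, and the table also on there being no responder among those removed: 0.2 to 1.3 points on the rate from the SAP-only exclusions, with a changed decision at a single responder count.

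A reader might infer three stronger things that the documents do not support:
- That the added exclusions necessarily inflate the rate. They do so only if removed patients respond less often than those kept; nothing in the documents shows that, and one removed responder can reverse the shift.
- That the primary test is invalid. It is a proper exact test of the rate among completely resected, scorable patients.
- That the SAP alone separates the primary rate from a rate for treated patients. The no-surgery exclusion is in the protocol as well.

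**What to change.** 1. Add a supportive exact test and one-sided 95% confidence interval for MPR in the full efficacy population, shown beside the primary result. Count no surgery or no scorable MPR as non-response, and score incompletely resected patients by their specimen where it can be scored. State this as an exception to the non-missing rule in SAP 6.1.1.
2. Define one DFS set: completely resected patients of the efficacy population, whether or not MPR can be scored. Make both paragraphs of SAP 6.3.3 and Table 3 agree with it.
3. Make protocol 6.4.2, SAP 6.3.2, Table 14.2.2.1 and Figure 1.1 name one population and one denominator.
4. List the two added exclusions in SAP 6.6, with reasons.

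The primary analysis can stay as it is. The cost is SAP wording and one table, plus a protocol clarification if item 3 is settled by changing protocol 6.4.2. The supportive rate may be lower than the primary rate.

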## 6. STATISTICAL METHODOLOGY

Data related to exploratory biomarker objectives will not be analyzed by Syneos Health and will not be mentioned further in this SAP.

### 6.1 Statistical and Analytical Issues

#### 6.1.1 Statistical Methods

Continuous data will be summarized by descriptive statistics, including mean, standard deviation, median, minimum, and maximum. Categorical data will be summarized by the number and percentage of subjects. Percentages will be based on non-missing data unless specified otherwise. Specific details regarding statistical testing will be found in Section 6.3 of this SAP.

Baseline values will be the latest assessment prior to the start of the first cycle of study drug. The same baseline will be used for each study phase.

Statistical analyses will be carried out using SAS® software version 9.3 or higher (Copyright, SAS Institute Inc. SAS and all other SAS Institute Inc. product or service names are registered trademarks or trademarks of SAS Institute, Inc., Cary, North Carolina, USA).

#### 6.1.2 Handling of Dropouts and Missing Data

##### Adverse Events

- Adverse events for which the relation to study drug is not reported will be assumed related to study drug.

- Adverse events for which the NCI CTCAE grade is not reported will not have a grade imputed and will be summarized as “No Grade”.
- Missing AE onset and end date components will be conservatively imputed for the purpose of determining treatment emergent status of any events with incomplete dates. Originally reported (and possibly missing or partial) onset and end date information will be presented listings. Imputation for missing AE date components will be handled as follows.
  - If only month and year are present for AE onset, the 1st day of the month and year will be imputed. If the available month and year of AE onset equal the month and year of date of first dose of study drug, and the resulting imputed date will not exceed an available complete end date of the event, then the date of the first dose of study drug will instead be imputed.
  - If only year is present for AE onset, the 1st day of January of the year will be imputed. If the available year of AE onset equals the year of date of first dose of study drug, and the resulting imputed date will not exceed an available complete end date of the event, then the date of the first dose of study drug will instead be imputed.
  - If only month and year are present for AE end, the last day of the month and year will be imputed (taking into account February in leap years). If the available month and year of AE end equal the month and year of study completion/discontinuation date, then the date of study completion/discontinuation will instead be imputed.
  - If only year is present for AE end, the 31st of December of the year will be imputed. If the available year of AE end equals the year of study completion/discontinuation date, then the date of study completion/discontinuation will instead be imputed.
  - AE onset and end dates which are entirely missing will not be imputed.
  - The chronological order of AE onset and end dates will be maintained.

#### Efficacy Analysis

Handling of missing data for efficacy analysis will be discussed in the respective sections below in this SAP.

#### **6.1.3 Pooling of Investigative Sites**

Data from all sites will be pooled for summarization and analyses.

#### **6.1.4 Determination of Sample Size**

The primary objective of this study is to determine the major pathological response rate. If there is evidence that the major pathologic response rate is at least 15% then there will be further consideration for the testing of atezolizumab in neoadjuvant lung cancer. This is a single-arm study, and all patients will be treated with atezolizumab. The primary endpoint is assessed by a statistical test of a single proportion of responders against the simple alternative of 5% response.

This design provides 95% statistical power to detect a difference of 10% (15% vs. 5%) at a significance level of 0.05 (1-sided test, variance of the test statistic calculated under the alternative hypothesis). To achieve this, approximately 180 patients will be enrolled in this study. At the final analysis (after 180 patients are enrolled), if there are at least 17 patients who respond then the statistical test rejects the null hypothesis of a 5% response rate in favor of a higher response rate.

This study includes one interim analysis to assess futility after 90 patients are assessed. The non-binding futility interim boundary satisfies conditional power of 0.30. Thus, the probability that the statistical test at the final analysis will be significant at the specified power and test level is at least 0.30, conditional on the data available at the time of the interim analysis. At the interim analysis, if there are seven or fewer responders out of 90 patients then the conditional power of the study drops below 0.30, and enrollment into the study may be terminated.

Differential response by PD-L1 status (positive versus negative) will be assessed. While the composition of PD-L1 status in this patient population is not known, the study will aim to include at least 60 PD-L1 positive patients. With 60 PD-L1 positive patients, the one-sided 95% CI excludes 20% if the major pathologic response rate is 30% (18 responders out of 60 patients). Final enrollment numbers may be expanded accordingly.

## 6.2 Subject Characteristics

### 6.2.1 Subject Disposition

#### Neoadjuvant Atezolizumab Therapy Phase

Calculating the percentages based on the number of subjects who received neoadjuvant atezolizumab treatment, summarize the following:

- The number of subjects who receive neoadjuvant atezolizumab (treated)
- The number and percentage of subjects who had surgery
- The number and percentage of treated subjects who completed Neoadjuvant Atezolizumab treatment
- The number and percentage of subjects who do not complete Neoadjuvant Atezolizumab treatment
- The number and percentage of subjects who do not complete Neoadjuvant Atezolizumab treatment by reason

#### Adjuvant Atezolizumab Therapy Phase

Calculating the percentages based on the number of subjects treated with adjuvant atezolizumab, summarize the following:

- The number of subjects who receive adjuvant atezolizumab (treated)
- The number and percentage of treated subjects who completed adjuvant atezolizumab treatment
- The number and percentage of subjects who do not complete adjuvant Atezolizumab treatment
- The number and percentage of subjects who do not complete adjuvant Atezolizumab treatment by reason

### Surveillance/Survival Follow-up Phase

Calculating the percentages based on the number of subjects entering the surveillance period, summarize the following by subgroup and overall:

- The number of subjects who enter the Surveillance/Survival Follow-up Phase
- The number and percentage of subjects who completed surveillance,
- The number and percentage of subjects who do not complete surveillance
- The number and percentage of subjects who do not complete surveillance by reason

Using subgroups:

- Subgroup A: No Adjuvant Treatment
- Subgroup B: Adjuvant Atezolizumab Treatment
- Subgroup C: SOC Chemotherapy ( $\pm$  Radiotherapy) Only
- Subgroup D: SOC Chemotherapy ( $\pm$  Radiotherapy) + Adjuvant Atezolizumab Treatment

